9. STATISTICAL CONSIDERATIONS AND DATA ANALYSES

9.1 Sample Size Determination

Approximately 280 healthy subjects will be screened to randomize at least 240 subjects to ensure 200 evaluable subjects complete the entire study. If no reaction is

| Document Name | Gsliki2070054pprot200 71585 | | |
|----------------------|---------------------------------------|---------------------|----------------------|
| Туре | Version | Document Identifier | Effective Date |
| eldo climitralleatoc | 0.0; CURRENT; Most-Recent; Registived | 090032d580e42556 | 31-Jan-2017 14:20:06 |
| Reason For Issue | Auto Issue | | |

observed in 200 subjects, there is a 95% certainty that the actual rate of reactions in the wider population is <1.8%.

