Type and Planned Number of Subjects

Approximately 280 healthy subjects will be screened to randomize at least 240 subjects to ensure 200 evaluable subjects complete the entire study. If no reaction is observed in 200 subjects, there is a 95% certainty that the actual rate of reaction in the wider population is <1.8%.

Diagnosis and Main Criteria for Inclusion

Healthy male and female volunteers aged 18 to 65 with no dermatological disorders, with a Fitzpatrick skin phototype I to IV will be enrolled into this study.

Product Information

| | Test Product | Reference Product | |
|--------------------------|---|--|--|
| Product Name | Facial micellar cleanser | Saline Solution: Sodium Chloride (NaCl; 0.9%) | |
| Product Formulation | CCI | N/A | |
| Code (MFC) | | Site to supply | |
| Product Format | 200ml clear PET Bottle N/A | | |
| Application Quantity | 0.02 millilitres/square | 0.02 ml/cm^2 | |
| | centimetre (ml/cm ²) | | |
| Route of Administration | Topical dermal application via semi occlusive patch | | |
| Application Instructions | Applied on-site by technician | | |

Statistical Methods

The focus of the statistical analysis will be the evaluation of the frequency and level of irritation and sensitisation responses of the investigational product. All subjects with any product applied will be included in the analysis population.

Individual observations will be assessed based on Appendix 2 and a narrative description of all skin responses, both in the induction and challenge phases, will be provided. A frequency tabulation of the number of subjects with any skin response versus those without any skin response will be presented by treatment group for both the induction and challenge phases of the study. If there are subjects with non-zero dermal response or superficial irritation scores, a combined dermal and others effects

| Document Name |   | | |
|----------------------|---|---------------------|----------------------|
| Туре | Version | Document Identifier | Effective Date |
| eldo climitralleatoc | 0.0; CURRENT; Most-Recent; Rfferietiwed | 090032d580e42566 | 31-Jan-2017 14:20:06 |
| Reason For Issue | Auto Issue | | |

score will be determined across all time points over the induction and challenges phases as well as at each assessment time point and summarised using descriptive statistics.

No interim or subgroup analyses are planned.

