9.3.2. Primary Analysis(es)

The primary analysis will be based on the irritation (dermal response) and superficial irritation (other effects) scores/grades assessed using the scales described in Tables 1 and 2 of Appendix 2. Individual observations will be assessed based on these scales and a narrative description of all skin responses, both in the induction and challenge phases, will be provided.

No formal statistical inference will be performed.

The number and percentage of subjects recording each category of score/grade, as well as any skin response versus those without any skin response will be presented by treatment group at each assessment time point and over the induction and challenge phases using the maximum grade/score. If there are subjects with non-zero dermal response or other effects scores, then the dermal response, other effects and a combined dermal and others effects score will be summarised using descriptive statistics at each assessment time point and over the induction and challenges phases using a total score across time points.

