12.2. Appendix 2 – Dermal Response Score

Any skin response at a patched site will be clinically assessed using the criteria recommended by the US Department of Health and Human Services Food and Drug Administration (FDA), 1999.

Any localised response to the patch application and removal that's typical to the procedure, won't be captured as an AE, unless more severe than expected in which case will be captured as an AE.

The following grades and their respective numerical equivalent scores will be used to express the response observed at the time of examination:

Table 1. Skin Irritation Scoring System

| Document Name | ©\$\text{circle17B65}\text{qurot} \text{207585} | | |
|-----------------------|---|---------------------|----------------------|
| Туре | Version | Document Identifier | Effective Date |
| eldo climitarelleatoc | 0.0; CURRENT; Most-Recent; Rfferietiwed | 090032d580e42d66 | 31-Jan-2017 14:20:06 |
| Reason For Issue | Auto Issue | | |

Table 2. Superficial Irritation Score (Symbols and Numerical Equivalents)

The results will be presented as individual responses to each test product and the negative control (saline solution) at each assessment time point. All responses will be reviewed in context of the grading scale.

Each of the scores represents an effect that is localised in a representative portion of the patch area, defined as 25% or more of the patch test site. Individual observations will be recorded in tables and a narrative description of all skin responses (any score >0) will be provided. Superficial irritation scores are only provided if there is a dermal response score >0.

Each Superficial Irritation Score should be reported as a letter. The combined score will equal the sum of the dermal response score plus the numerical equivalent of the superficial irritation score (e.g. dermal response score=3 and superficial irritation letter="C" implies a combined score of 3 + 2 = 5).

If a subject develops a combined score of 3 or greater at any point during the Induction phase, the patch will be applied to an adjacent naïve site for the next application. If a combined score of 3 or greater occurs at the naïve site, no further patch applications will be made. Such reactive subjects will, however, receive patches on naïve test sites during the challenge phase of the study unless, in the opinion of the Investigator, it would be unwise to do so.

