2.4 Analysis of Dermal Responses

2.4.1 Primary endpoint

2.4.1.1 Primary endpoint definition

The primary analysis will be conducted to assess the cutaneous irritation and sensitisation potential of the test and control product, based on the combined irritation (dermal response) and superficial irritation (other effects) score/grade after patch removal during the induction and challenge phases using the ITT population.

Calculation of combined score (dermal response and superficial irritation):

Document Name	gsk-207585-reporting-and-analysis-plan		
Type	Version	Document Identifier	Effective Date
eldo_controlled	0.1; CURRENT; Most-Recent; Reviewed	090032d580e125d0	
Reason For Issue			

GSK Consumer Healthcare

Confidential

Page 10

Statistical Analysis Plan

207585

The combined score for dermal response and superficial irritation (other effects) will be calculated in the following way –

Combined score = dermal response score + numerical equivalent of the superficial irritation score

Where, the dermal response scale is described in the Table 2 below, and the superficial irritation scores in Table 3 below.

Table 2: Skin Irritation Scoring System (Dermal Response)

CII

Table 3: Superficial Irritation Score System (Symbols and numerical Equivalents)

CII

* The letter grades assigned to the irritation responses will be converted to scores for the statistical analysis process. Grading will be conducted throughout the trial by a qualified staff member.

For example, if the dermal responses score=3 and superficial irritation letter ="C" then the combined score will be:

Combined score = 3 + 2 = 5

 GlaxoSmithKline	Document Name	gsk-207585-reporting-and-analysis-plan		
	Type	Version	Document Identifier	Effective Date
	eldo_controlled	0.1; CURRENT; Most-Recent; Reviewed	090032d580e125d0	
	Reason For Issue			

GSK Consumer Healthcare

Confidential

Page 11

Statistical Analysis Plan

207585

Only subjects with at least one combined score > 0 at any visit will be summarised. The frequency of scores will be summarized in each category of combined score by treatment group and at each time point for both induction and challenge phases. The maximum combined score irrespective of visits for each phase will also be presented ([Table 14.2.1.1](#)). No formal statistical inference will be performed.

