2.8 Sample size calculation

Approximately 280 healthy subjects were screened to randomize at least 240 subjects to ensure 200 evaluable subjects complete the entire study. If no reaction is observed in 200 subjects, there is a 95% certainty that the actual rate of reactions in the wider population is <1.8%.

3 Changes to the Protocol Defined Statistical Analysis Plan

There were no changes or deviations to the originally planned statistical analysis specified in the [protocol version 1.0 \[\(Dated: 31/JAN/2017\)\]](#).

 GlaxoSmithKline	Document Name	gsk-207585-reporting-and-analysis-plan		
	Type	Version	Document Identifier	Effective Date
	eldo_controlled	0.1; CURRENT; Most-Recent; Reviewed	090032d580e125d0	
	Reason For Issue			

4 Appendix 1:

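### The SAP shells do not secure the protocol's any-response tabulation, and no planned output reports the reaction-rate limit used to justify 200 subjects

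*Protocol*

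**What the plan says.** **Sizing.** Protocol 9.1 says that, with no reaction "observed in 200 subjects, there is a 95% certainty that the actual rate of reactions in the wider population is <1.8" per cent. The synopsis, protocol 3.3 and SAP 2.8 repeat this. None of the four places names a method, says whether the limit is one- or two-sided, or defines a reaction.

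**Protocol tabulation.** The synopsis states: "A frequency tabulation of the number of subjects with any skin response versus those without any skin response will be presented by treatment group". This covers induction and challenge. Section 9.3.2 adds each score category and "any skin response versus those without any skin response will be presented by treatment group at each assessment time point", plus the maximum over each phase. Only the descriptive statistics of the scores depend on someone having a non-zero score. Appendix 2 also promises individual data: "The results will be presented as individual responses to each test product and the negative control (saline solution) at each assessment time point".

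**SAP.** Section 2.4.1.1 says of the combined score: "Only subjects with at least one combined score > 0 at any visit will be summarised". In section 5.1, the programming notes to Tables 14.2.1.1, 14.2.2.1 and 14.2.2.2 require each table only when at least one subject has a score above zero. The notes assign Visits 2 to 10 to induction, Visit 11 to rest and Visits 12 to 15 to challenge. Section 4.3 contains no listing of patch scores. Section 3 declares no departure from the protocol's analysis.

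**The concern.** The trial has no hypothesis test. Its quantitative claim is how high the reaction rate could still be after the observed result, and that depends on two numbers: how many reacted and how many were assessed. The protocol undertakes to show reactors and non-reactors. The SAP leaves it open whether that table is produced, which subjects it covers and which readings count.

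The inconsistency is sharpest for a completely clean result, which is the case the sizing sentence describes. The report could then contain no table showing zero reactors over the number assessed in induction and in challenge. When reactions do occur, the tables appear, but their phase summaries mix pre-patch with post-patch readings and the induction summary lacks the last induction-patch reading. In neither case does any output give the limit that justified the sample size.

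**Working it through.** **1. Reproducing the plan's figure.** Inputs from protocol 9.1: 0 reactions, n = 200, 95%.
- Exact two-sided upper limit: 1 − 0.025^(1/200) = 0.01828, or 1.83%.
- Exact one-sided bound: 1 − 0.05^(1/200) = 0.01487, or 1.49%.
- One-sided confidence carried by 1.8%: 1 − 0.982^200 = 0.974.

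The stated figure matches the rounded two-sided exact limit. That origin is inferred; a uniform-prior 95% interval gives 1.82%. Read one-sided, the sentence is true and conservative.

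**2. When the tables lapse.** Appendix 2 states: "Superficial irritation scores are only provided if there is a dermal response score >0". With no dermal score above zero, the combined and superficial scores are therefore also zero, and all three notes apply together. One non-zero dermal score at either site, saline included, brings back Tables 14.2.1.1 and 14.2.2.1 with both product columns. Table 14.2.2.2 can lapse alone, because superficial grade A carries a score of 0. The SAP's rule for empty output covers listings only, and narratives cover only scores above zero.

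**3. How likely an all-zero study is.** Let q be the chance that a subject has any non-zero score at either site. The documents give no value, so q is assumed. With 240 subjects assessed and independent, P(all zero) = (1 − q)^240:
- q = 0.5%: 0.300
- q = 1%: 0.090
- q = 2%: 0.008

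**4. Which subjects.** Taken literally, the SAP 2.4.1.1 sentence removes non-reactors from the combined-score summary. Yet the shell for Table 14.2.1.1 has a score-0 row at each visit and a row for subjects with no combined score above zero. Both cannot be followed.

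**5. Which readings.** Schedule of Events notes g and h place the Visit 2 and Visit 12 readings before patch application. The nine induction patches are read at Visits 3 to 11.
- Shell induction block, Visits 2 to 10: one baseline reading plus eight of the nine post-patch readings.
- Shell challenge block, Visits 12 to 15: one pre-patch reading plus the three post-patch readings.

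The protocol disagrees with itself on Visit 11. Schedule note e and section 6.2.2 treat it as induction; the patch-assessment text in section 3.4 counts it under rest. The shells follow 3.4, so the induction maximum omits the reading after the ninth patch.

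**6. What the missing limit would show.** Exact two-sided 95% intervals at n = 200:
- 1 reactor: 0.01% to 2.75%
- 2 reactors: 0.12% to 3.57%
- 3 reactors: 0.31% to 4.32%

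The denominator matters too. For zero reactors, 1 − 0.025^(1/n) gives 2.03%, 1.83%, 1.66% and 1.53% at n = 180, 200, 220 and 240 (180 and 220 are illustrations).

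**The case against.** The strongest reply has five parts.

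- **No inference is planned.** Protocol 9.3.2 and SAP 2.4.1.1 rule out formal inference, and neither document promises an interval. This stands in part: leaving out the limit breaks no commitment. But the sizing sentence is itself a confidence statement, and an interval labelled descriptive tests nothing.
- **An all-zero study is remote.** Protocol 3.4 describes patch-site reactions as expected under these conditions, and the lowest positive dermal grade is barely visible redness. This stands. The notes also say when a table is required; they do not forbid producing it otherwise.
- **The denominator is not lost.** Table 14.1.1 reports completers regardless of scores, and protocol 4.6 defines a completer as someone who finished all phases. This largely stands. A reader might infer that a clean result would leave the sizing statement with no denominator at all; it would not. What is missing is the number assessed in each phase.
- **The restricting sentence is loose drafting.** Probably so, given the shell's own rows. A reader might infer that non-reactors are to be dropped from the analysis; the shell does not support that. The text still needs correcting, because it conflicts with the shell it introduces.
- **Visit 11 under rest has protocol support.** It does, in section 3.4. The SAP did not invent the allocation; the protocol has to be reconciled.

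The conflict between the shell notes and the protocol's unconditional tabulation survives, as does the missing listing.

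**Conclusion.** The concern holds as a reporting and specification gap that should be corrected before unblinding. The three notes and the restricting sentence contradict the protocol's unconditional tabulation. The phase blocks do not isolate post-patch readings. The promised individual responses have no listing. SAP section 3 nevertheless declares no changes. Separately, the one quantity used to justify 200 evaluable subjects is never reported.

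A reader might infer that the 1.8% figure is wrong or that the trial is mis-sized. The documents do not support that: 0/200 gives 1.83% two-sided and 1.49% one-sided, and n does not change.

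The practical weight is moderate. Complete loss of the tables needs zero scores at both sites in every subject, with probability 30%, 9% or 0.8% under the assumed q of 0.5%, 1% or 2%. The restricting sentence, the visit allocation and the absent limit and listing apply whatever the result.

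**What to change.** 1. Delete the three conditional programming notes and the SAP 2.4.1.1 sentence restricting the summary to subjects with a positive combined score, so that 0/N is always shown.
2. In Table 14.2.1.1 add, by product and phase, subjects with any post-application dermal score above zero over subjects with at least one post-application score in that phase. Give the two-sided exact (Clopper-Pearson) 95% interval, labelled descriptive. Use Visits 3 to 11 for induction, after reconciling Schedule note e with protocol 3.4, and Visits 13 to 15 for challenge.
3. As a supportive line, restrict both numerator and denominator to study completers (protocol 4.6), the basis of the sizing sentence, and list separately any reactor who did not complete. Do not add reactors back into a complete-readings set: that selects on outcome and biases the rate upward.
4. Add a patch-score listing by subject, product and visit to SAP 4.3.
5. Optional: in the four places, label the sizing figure as the exact two-sided 95% upper limit (1.83%), to match the table.

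The cost is three notes and one sentence removed, two lines per phase, one listing and one reconciliation of protocol text. Sample size and study conduct do not change. The downside is slightly more output, and a less favourable limit on display if reactions occur.

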9.2. General Considerations

9.2.1. Definition of Analysis Populations

The 'Intent to treat' (ITT) population includes all subjects who are randomised into the study and have skin irritation scores from at least one of the test sites available.

A separate Per Protocol (PP) analysis will not be performed. Protocol deviations will however be listed for review.

The Safety population includes all subjects who received any application of the study products. All safety analyses will be performed using the Safety population.

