4.6. Subject and Study Completion

A completed subject is one who has completed all phases of the study including the follow-up visit.

The end of the study is defined as the date of the last subject's last visit.

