9.2.3. Criteria for Evaluation

The primary evaluation will be to assess the cutaneous irritation and sensitisation potential of the test and control product, based on the irritation (dermal response) and superficial irritation (other effects) score/grade after patch removal during the induction and challenge phase using the ITT population.

Safety and tolerability will be evaluated by adverse events assessments using the Safety population.

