9.2.4. Handling of Dropouts and Missing Data

Missing data will not be replaced or imputed. Dropouts will be included in analyses up to the point of discontinuation.

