2.1 Populations for analysis

2.1.1 Subject disposition

Screen failures will be defined as subjects who do not satisfy all the inclusion/exclusion criteria. A summary will be provided of the number of subjects screened and the number of screen failures with reasons why subjects were not randomised.

Subject disposition will be summarized as the number and percentage of subjects (out of the number of randomised subjects) who complete the study, with the number who discontinue broken down by reason for discontinuation (Table 14.1.1). The table will also summarize the number and percent of subjects assigned to each analysis population (refer to section 2.1.3).

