2.4.2 Handling of missing values/censoring/discontinuations

Missing data will not be replaced or imputed. Dropouts will be included in analyses up to the point of discontinuation.

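### The SAP score tables count pre-patch grades as responses and are not required if nobody reacts, contrary to the protocol's primary evaluation

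*Protocol*

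**What the plan says.** **Endpoint.** Protocol 9.2.3 bases the primary evaluation on the "score/grade after patch removal during the induction and challenge phase using the ITT population". SAP 2.4.1.1 repeats this: "after patch removal during the induction and challenge phases using the ITT population". ITT (protocol 9.2.1, SAP 2.1.3) takes randomised subjects who "have skin irritation scores from at least one of the test sites available".

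**Timing of two grades.** Notes g and h to the Schedule of Events in the protocol put the Visit 2 grading before the first induction patch and the Visit 12 grading of the naïve site before the challenge patch.

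**Table rules.** The programming notes to SAP Tables 14.2.1.1, 14.2.2.1 and 14.2.2.2 start induction at Visit 2 and challenge at Visit 12. The phase maximum is taken over all visits of the phase. Each table is needed only if at least one subject scores above 0. SAP 2.4.1.1 adds that only subjects with a combined score above 0 are summarised. Protocol 9.3.2 sets no such condition on the comparison of subjects with and without a response; it attaches the non-zero condition only to the descriptive statistics. SAP section 3 declares no change from the protocol.

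**Numbers.** Protocol 9.1 plans to randomise at least 240 "to ensure 200 evaluable subjects complete the entire study", and says that no reaction in 200 gives 95% certainty of a true rate below 1.8%. Protocol 4.6: "A completed subject is one who has completed all phases of the study including the follow-up visit". SAP 2.1.1 reports the "number and percentage of subjects (out of the number of randomised subjects) who complete the study". Protocol 9.2.4: "Dropouts will be included in analyses up to the point of discontinuation". SAP 2.4.2: "Missing data will not be replaced or imputed".

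**The concern.** The primary result is a descriptive frequency with no formal inference, so the rules that decide who is counted as a responder, and out of how many, are in effect the analysis.

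Three things are at stake. First, a grade on skin that no product has touched cannot be a response to product, yet the table notes count it as one, at whichever product's site it falls. Second, the table that would document a clean result is the one that may be omitted when the result is clean. Third, sensitisation can be read only in subjects who were challenged and graded after removal, and the tables do not say whether the challenge percentages are taken over those subjects.

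**Working it through.** **1. Pre-patch grades.** Set side by side, the endpoint starts after patch removal, while the notes' phases start at Visits 2 and 12, both graded before application. The any-score-above-0 rows and the phase maximum run over every visit in the phase, so both absorb the pre-patch grade. For a subject graded above 0 at Visit 12 and 0 at Visits 13 to 15:
- Added to the challenge response rate, assuming 200 read: 1/200 = 0.50 percentage points.
- The same event at Visit 2, assuming 240 in ITT: 1/240 = 0.42 points on the induction rate.

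**2. The plan's own figure.** The two-sided exact 95% upper limit for 0/n is 1 − 0.025^(1/n). For n = 200 this is 1.828%, which rounds to the stated 1.8%. The one-sided version, 1 − 0.05^(1/200), gives 1.487%, so the two-sided basis is the one that matches.

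**3. What remains if nobody scores above 0.** All three score tables lapse under their own notes. SAP 4.3 lists no listing of individual scores. Table 14.1.1 remains; its Completed row gives a count and a percentage of randomised subjects, but not the number graded after removal. The number matters to the statement:

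| Subjects read, no reaction | Two-sided exact 95% limit |
|---|---|
| 190 | 1.92% |
| 200 | 1.83% |
| 210 | 1.74% |
| 220 | 1.66% |
| 230 | 1.59% |
| 240 | 1.53% |

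The SAP plans no such limit for reporting; the table only shows how far the statement depends on the number read.

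**4. Internal conflict.** The shell of Table 14.2.1.1 has a score-0 row at each visit and a row for subjects with no score above 0. Neither can be filled if only subjects with a score above 0 are summarised, as SAP 2.4.1.1 says.

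**5. Challenge base (conditional).** The shell is drawn for induction, with two complementary n (%) rows under the ITT N and no row for subjects not assessed. Suppose challenge repeats this layout, 240 are in ITT and r are read. Rates are then understated by 1 − r/240:
- r = 200: 1 − 200/240 = 16.7% relative. One reactor shows as 1/240 = 0.42% instead of 1/200 = 0.50%, a difference of 0.08 points.
- r = 190, 210, 220, 230: 20.8%, 12.5%, 8.3%, 4.2%.

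**The case against.** The strongest reply is that the plan says more than this point credits, and that the effects are small.

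- *A reader might infer that challenge has no denominator at all.* That is not so: both documents name ITT. What is missing is a challenge-specific percentage base.
- *A reader might infer that unread subjects are planned to count as non-reactors.* The documents do not say so. It follows only from extending an induction shell to challenge, and it would sit badly with the no-imputation and dropout rule. That rule, however, is not carried into the shell, and it does not clearly cover a subject who stays in the study unchallenged, which protocol 5.2 allows for some induction reactors.
- *A reader might infer that the <1.8% statement has no defined basis.* Evaluable is not defined, but the sentence speaks of completing the study and protocol 4.6 defines a completer, so completers are the natural reading. Nor is the statement limited to challenge reactions.
- *The tables lapse only in a narrow case.* This stands. One score above 0 in either phase triggers production. With nobody above 0, the provision for withholding challenge after an induction reaction cannot operate, so the Completed count should be close to the number graded.
- *Much is visible anyway.* When a table is produced, Visit 12 has its own rows, and summing the score rows gives the number read at each visit. The number with any reading across Visits 13 to 15 cannot be recovered that way. Protocol 3.4 and 6.2.2 promise individual responses at each time point, but the SAP index lists no output for them.
- *A mark on screened, healthy, unpatched skin should be rare.* Agreed. That limits the size, not the conflict.

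**Conclusion.** Two parts hold on the text alone. The table notes count pre-patch grades as responses, against an endpoint defined after patch removal. The SAP also makes conditional a presentation that the protocol requires unconditionally, while declaring no change. The first costs 0.50 percentage points per Visit 12-only grade, assuming 200 read. The second leaves the zero-reaction case without a reported count of subjects graded after removal; Completed is the nearest figure.

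The denominator part is conditional and small: 0.08 points for one reactor, assuming 240 in ITT, 200 read and percentages on the ITT N. Each subject receives both products, so the test-versus-saline contrast is largely unaffected by it. The documents do not support reading it as a planned dilution of the challenge rate. The 1.8% figure itself reproduces.

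**What to change.** Before unblinding, amend the SAP as follows:

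1. Report Visits 2 and 12 as pre-patch baselines, still displayed, but outside the phase response counts and maxima. This applies to all three score tables.
2. Produce the response tables even when every score is 0, and delete the SAP 2.4.1.1 sentence that restricts the summary to subjects scoring above 0.
3. Show the number assessed at each visit. Base challenge percentages on ITT subjects with at least one post-removal challenge reading (Visits 13 to 15), so that a reactor who then drops out is kept. Add a row for subjects not assessed at challenge, with reasons.
4. State that evaluable means completers with all three post-removal challenge readings, and report that number beside any zero-reaction statement.
5. Record these points in SAP section 3. Note there that every grade is still displayed, so the protocol 9.2.2 rule against excluding data still holds.

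The cost is SAP wording and a few table rows, with no new data. Challenge percentages may become slightly less favourable.
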